# 10. Records, Confidentiality and Data Monitoring

Each patient will be identified by a study ID number only in the trial records. Study data will be recorded on pre-printed case report forms (CRFs). Monitoring of study data recorded on source documents and reported on study CRFs will be conducted for all patients to ensure accuracy and completeness. All data will be stored on a HIPAA compliant online resource.

## **11. Quality Control and Assurance**

Complete and accurate data collection and reporting will be the responsibility of the Principle Investigator.

## **12. Good Clinical Practice**

This investigation will be conducted in accordance with the International Conference on Harmonization (ICH) E6 for Good Clinical Practice (GCP): Consolidated Guidance and all appropriate regulatory requirements. The Investigator will be thoroughly familiar with the appropriate use of the treatment procedure as described in the protocol. Essential clinical documents will be maintained to demonstrate the validity of the study and the integrity of the data collected. Master files will be established by the site personnel at the beginning of the study, maintained for the duration of the trial and retained according to all appropriate regulations.

#### **13. Ethical Considerations**

The study will be conducted in accordance with ethical principles founded in the Declaration of Helsinki. The Institutional Review Board (IRB) will review all appropriate study documentation, including the protocol, informed consent and any advertisements that will be used for the study in order to safeguard the rights, safety and wellbeing of the patients. The study will only be conducted once IRB approval has been obtained. The Investigator will provide safety updates, annual progress reports and any revisions to these documents to the IRB as required by regulations.

#### 14. Patient Information and Informed Consent

After the study has been fully explained to each patient in their preferred language, written informed consent (also in the patient's preferred language) will be obtained from each patient prior to any study-specific procedures being performed. The IRB will approve the informed consent form prior to use. The method of obtaining and documenting the informed consent and the contents of the consent will comply with ICH-GCP and all other applicable regulatory requirements.

# **15. Patient Confidentiality**

In order to maintain patient privacy, all case report forms (CRFs), study reports and communications will identify the patient by their assigned study ID only. The patient's confidentiality will be maintained and will not be made publically available to the extent permitted by the applicable laws and regulations.

#### 16. Retention of Study Data

University of California Los Angeles (UCLA) Medical Center will retain the written and/or electronic medical records, reports and data relating to the study in a secure location for a period of ten (10) years. UCLA Medical Center will prepare and maintain accurate written records of and data from the study.

# **Appendix A: Schedule of Study Events**

	Visit 1	Visit 2	Visit 3	Visit 4	Visit 5	Visit 6	Visit 7	
	Screening (within 8 weeks of Day 1)	Treatment (Day 1)	Week 1 (day 4-10)	Month 1 (4 weeks ± 2 weeks)	Month 3 (12 weeks ± 2 weeks)	Month 6 (24 weeks ±2 weeks)	Month 12 (52 weeks ± 2 weeks)	
Informed Consent	Х							
Eligibility criteria assessment	X							
Demographics	X							
Medical History	Х							
Concurrent Medical Conditions	Х							
Physical Examination	X		Х	Х	Х	Х	Х	
Vital Signs	Х		Х	Х	Х	Х	Х	
Laboratory Evaluations 	Х							
WOMAC	X			Х	Х	Х	Х	
VAS	Х			Х	Х	Х	Х	
PRO and PGIC							Х	
Knee x-ray 	Х						Х	
Knee MRI 	X				Х			
GAE		Х						
Adverse Events		Х	Х	Х	Х	Х	Х	
Concomitant Medications	X	X		X	X	X	X	
Protocol violations	X	Х	Х	Х	Х	Х	Х	

 Laboratory evaluations include complete blood count and serum chemistry

 Screening knee X-Ray can be performed within 6 months before Visit 1.

 Screening knee MRI can be performed within 6 months before Visit 1. If patients cannot undergo MRI (e.g. pacemaker, significant claustrophobia), then CT of the knee without contrast will be performed.

## Appendix C: Technical Protocol for Genicular Artery Embolization

- Immediately prior to the procedure, appropriate knee will be marked. Discern areas of focal point tenderness (up to 3 locations) and place radio-opaque BB marker.
- Administer prophylactic IV antibiotics, based on institution standard of care. Choice of antibiotic and sedation will be at the discretion of the interventional radiologist.
- Local anesthesia should be administered for a transfemoral approach on the side with the best arterial pulse, preferably on the same side as the affected knee.
- Access of the common femoral artery with a 21-gauge needle, with exchange to a 3-5 French sheath
- Angiogram of the superficial femoral artery (thigh)
- Catheterization of the distal superficial femoral artery, with repeat angiogram.
- Intraprocedural rotational c-arm CT of the knee with concurrent contrast injection in the distal superficial femoral artery
- Selective catheterization of the specific genicular arteries that are supplying the areas of the patient's pain, with repeat angiogram.
- If hypervascularity is seen, embolization is performed with 100 micron Embozene particles, suspended in a diluted solution of contrast and saline.
- Procedural endpoint is lack of distal hypervascularity, with preservation of normal arterial flow. Arterial stasis should not be achieved.
- Perform follow up angiography after each vessel is embolized to evaluate genicular devascularization and to identify any remaining collateral blood supply to the knee.
- Once the embolization procedure is complete, follow institution's standard of care for catheter and introducer removal and closure of femoral puncture. This will typically be done with manual compression.
- It is suggested that patients be discharged with and oral non-opioid analgesic, 4-6 hours after the procedure.

# Appendix D: Western Ontario and McMaster Universities Osteoarthritis Index (WOMAC, version 3.1)

Instructions: Please rate the activities in each category according to the following

scale of difficulty: 0 = None, 1 = Slight, 2 = Moderate, 3 = Very, 4 = Extremely

Circle one number for each activity

Pain	1. Walking	0	1	2	3	4
	2. Stair Climbing	0	1	2	3	4
	3. Nocturnal	0	1	2	3	4
	4. Rest	0	1	2	3	4
	5. Weight bearing	0	1	2	3	4
Stiffness	1. Morning stiffness	0	1	2	3	4
	2. Stiffness occurring later in the day	0	1	2	3	4
Physical Function	1. Descending stairs	0	1	2	3	4
	2. Ascending stairs	0	1	2	3	4
	3. Rising from sitting	0	1	2	3	4
	4. Standing	0	1	2	3	4
	5. Bending to floor	0	1	2	3	4
	6. Walking on flat surface	0	1	2	3	4
	7. Getting in / out of car	0	1	2	3	4
	8. Going shopping	0	1	2	3	4
	9. Putting on socks	0	1	2	3	4
	10. Lying in bed	0	1	2	3	4
	11. Taking off socks	0	1	2	3	4
	12. Rising from bed	0	1	2	3	4
	13. Getting in/out of bath	0	1	2	3	4

14. Sitting	0	1	2	3	4
15. Getting on/off toilet	0	1	2	3	4
16. Heavy domestic duties	0	1	2	3	4
17. Light domestic duties	0	1	2	3	4

Pain Score (1-5): \_\_\_\_\_

Total Score: \_\_\_\_\_

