## Rationale

The knee receives its blood supply from the genicular arteries, branches from the superficial femoral and popliteal arteries. Deliberate partial blockage of the genicular arteries (embolization) leads to reduction of the inflammatory response, with potential improvement in pain. Recently, Okuno and colleagues reported their experience with genicular artery embolization for patients with mild-to-moderate knee osteoarthritis. In their pilot study, 14 patients underwent embolization (7). No major adverse events were reported. There was a dramatic and rapid reduction in symptom and pain scores of patients.

In 2017, the same authors reported their results of genicular artery embolization performed on 95 knees in 72 patients (6). All patients had pain that was resistant to conservative treatment, such as oral nonsteroidal ant-inflammatory drugs, oral opioid agents, physical therapy, stretching, muscle strengthening, or intraarticular injection of hyaluronic acid. The distribution of local tenderness (indicating the presence of inflammation) was evaluated in all cases immediately before transcatheter arterial embolization and subdivided into eight areas to determine the key arteries to be treated. After selective catheterization of the appropriate genicular artery, imipenem/cilastatin sodium was used as the embolic material in 88 knees in 65 patients. Patients who had contraindications to imipenem/cilastatin (ie, a history of hypersensitivity or allergy to antibiotic agents or treatment with valproic acid) were treated with 75-µm Embozene microspheres instead (7 knees in seven patients).

Mean Western Ontario and McMaster Universities Osteoarthritis Index (WOMAC) pain scores decreased significantly from 12.1 at baseline to 6.2 at 1 month, 4.4 at 4 months, 3.7 at 6 months, 3.0 at 12 months, and 2.6 at 24 months after the first transcatheter arterial embolization procedure (all P < .001). The intent-to-treat clinical success rate at 6 months of follow-up was 86.3% (95% CI, 78%–92%). The mean total WOMAC score also decreased significantly from 43 at baseline to 24, 14.8, 11.2, 8.2, and 6.2 at 1, 4, 6, 12, and 24 months, respectively (all P < .001). The mean VAS score significantly decreased from 72 at baseline to 38, 29, 19, 13, and 14 at 1, 4, 6, 12, and 24 months, respectively (all P < .001). Patients reported a decrease in the dose of medication used and frequency of other treatments after the procedure.

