#### 3.2 Exclusion Criteria

Subjects that meet any of the following exclusion criteria will not be eligible for this study:

- Mild knee pain as determined by visual analog scale < 4
- Chronic renal insufficiency (serum creatinine >2 mg/dL)
- Uncorrectable bleeding diathesis
  - INR >1.6
  - Platelets <50,000
- Significant arterial atherosclerosis that would limit selective angiography
- Allergy to iodinated contrast agents that is not responsive to steroid management
- Active Infection or malignancy
- Appropriate candidate for knee replacement surgery determined by clinical and physical examination
- Recent (within 3 months) or active cigarette use
- Prior knee arthroplasty surgery in the subject knee
- Active pregnancy

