# 8. Symptom Assessment

8.1 Western Ontario and McMaster Universities Osteoarthritis Index (WOMAC, version 3.1)

The Western Ontario and McMaster Universities Osteoarthritis Index (WOMAC) is a widely used, set of standardized questionnaires used by health professionals to evaluate the condition of patients with osteoarthritis of the knee and hip, including pain, stiffness, and physical functioning of the joints. It can be self-administered and was developed at Western Ontario and McMaster Universities in 1982.

The WOMAC measures five items for pain (score range 0–20), two for stiffness (score range 0–8), and 17 for functional limitation (score range 0–68). Physical functioning questions cover everyday activities such as stair use, standing up from a sitting or lying position, standing, bending, walking, getting in and out of a car, shopping, putting on or taking off socks, lying in bed, getting in or out of a bath, sitting, and heavy and light household duties.

A WOMAC test takes about 12 minutes, and is among the most widely used assessments in arthritis research.

A copy of the WOMAC (version 3.1) is provided in Appendix D.

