#### Efficacy Analyses

The primary is the change in WOMAC before GAE to 12 months after GAE. All statistical tests and confidence intervals (CIs) will be two-sided with a nominal significance level of p < 0.05 (95% confidence). A linear mixed model (LMM) will be used to test for the mean change in WOMAC while adjusting for potential site-effects. The baseline and 12 month observations will be included in the model. The dependent variable will be the changes in WOMAC and the independent variables will be the WOMAC at baseline, baseline severity (moderate/severe arthritis), indicators of time (fixed effect  $\Delta$ ) and random intercepts for patient and site. The parameter  $\Delta$  corresponds to the mean change in WOMAC. A Wald-type test of  $\Delta = 0$  and 95% CI of  $\Delta$  will be calculated.

Secondary analyses will also include analyzing changes from baseline to other timepoints and between post-treatment timepoints using the same methods. The Kaplan-Meier curves will be used to analyze the time until WOMAC improvement is first observed (i.e. time to improvement). The Turnbull method will be used to estimate these curves while accounting for interval censoring (the clinical improvement event is only known to have occurred between the current and prior visit).

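### The WOMAC form and analysis name no index knee, so the 12-month efficacy change may partly reflect a knee that GAE did not treat

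*Combined protocol and SAP*

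**What the plan says.** **Treatment and eligibility are knee-specific.** Appendix C begins: "Immediately prior to the procedure, appropriate knee will be marked". Section 3.2 excludes "Prior knee arthroplasty surgery in the subject knee", which leaves prior arthroplasty of the other knee allowed. It also excludes an "Appropriate candidate for knee replacement surgery determined by clinical and physical examination", with no side given.

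**The outcome is not.** Section 8.1 presents the WOMAC as a tool to "evaluate the condition of patients with osteoarthritis of the knee and hip" and sets no index joint. The form in Appendix D has 24 items (5 pain, 2 stiffness, 17 function). Its instruction is "Instructions: Please rate the activities in each category according to the following", followed by the scale; no knee or side appears anywhere on it.

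**Nor is the analysis.** Section 9 states: "The primary is the change in WOMAC before GAE to 12 months after GAE". In the mixed model, "the independent variables will be the WOMAC at baseline, baseline severity (moderate/severe arthritis), indicators of time", with random intercepts for patient and site. There is no term or rule for the status or treatment of the other knee.

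**Background.** The 2017 series cited in the Rationale reports "genicular artery embolization performed on 95 knees in 72 patients".

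**The concern.** The treatment acts on one knee, while the form asks about walking, stairs, night pain and similar activities for the patient as a whole. A patient with two painful knees must decide which one to score, and may not decide the same way at baseline and at month 12.

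Two biases can follow, in opposite directions:

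- **Dilution.** If the other knee stays painful, the score falls by less than the treated knee improved. If the worse knee was treated and GAE works, the other knee may become the main source of pain, so dilution could be greatest where GAE does best.
- **Inflation.** If the other knee is injected or operated on during follow-up, the WOMAC may fall for that reason. In a single-arm before-after design the gain is counted as GAE effect.

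Neither is removed by the mixed model. The time-to-improvement analysis uses the same scores and inherits the problem.

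**Working it through.** The documents give no WOMAC effect size, standard deviation or power, so there is no stated figure to reproduce. The check is of the text first, then an illustration.

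**1. Is an index knee set anywhere for the WOMAC?** The form (Appendix D), the instrument description (Section 8.1) and the analysis (Section 9) do not set one. The global-impression question in Appendix G also gives no side. The VAS form (Appendix E) is not in the text available, so it cannot be judged.

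**2. Is the other knee kept out by eligibility or follow-up rules?** No criterion in Section 3 excludes symptomatic osteoarthritis of the other knee. The knee-replacement-candidate exclusion names no side and could remove some patients whose other knee is advanced, but it applies at screening only. No section limits treatment of the other knee during the 12 months. Appendix A schedules concomitant medications, medical history and concurrent conditions, but has no row for procedures on the other knee.

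**3. Is bilateral disease realistic?** From the cited series, assuming at most two knees per patient:

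- patients with both knees treated = 95 − 72 = 23
- share = 23/72 = 31.9%
- the same share of 40 patients = 0.319 × 40 = 12.8, about 13

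This is a share of patients treated on both sides in another population. It is not a rate for this trial.

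**4. Illustration of dilution.** Let b be the share with a symptomatic other knee and w the share of the change lost in those patients. Both are assumed. Then

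proportional shrinkage = b × w.

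The points column applies this to the total WOMAC change in the cited series, 43 − 8.2 = 34.8 points at 12 months.

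| b | w | b × w | 34.8 × (1 − b × w) |
|---|---|---|---|
| 0 | any | 0% | 34.8 |
| 0.32 | 0.25 | 8% | 32.0 |
| 0.32 | 0.50 | 16% | 29.2 |
| 0.75 | 0.25 | 19% | 28.3 |
| 0.75 | 0.50 | 38% | 21.8 |

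The range of w is illustrative and not a bound. A patient who scores the treated knee at baseline and the other knee at month 12 records the difference between two different knees, which could take almost any value.

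**5. Illustration of inflation.** If k of 40 patients gain g points from treatment of the other knee, the mean change rises by k × g/40. With g = 10 (assumed), this runs from 0 for k = 0 to 4 × 10/40 = 1.0 point for k = 4.

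**The case against.** The case on the other side is substantial.

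- **The size is not known.** This stands. The documents give neither this trial's share of bilateral disease nor how patients answer an unanchored form. A reader might take 16% as an estimate of the bias; it is one cell of an assumed table. A confidence interval around 23/72 would cover sampling error in the cited series only.
- **The other knee is not wholly unrestricted.** This stands in part. The side-neutral exclusion of knee-replacement candidates, and the requirement that patients be ineligible for or refuse surgery, may keep out some patients heading for arthroplasty of either knee. They do not exclude milder disease there, or limit injections or later procedures.
- **A comparator arm is not the remedy for dilution.** This stands. Scores reflecting an untreated knee would shrink a between-arm difference too. The single-arm design worsens only the inflation route.
- **Some information is already collected.** History, concurrent conditions, medications and examinations could reveal other-knee disease. No analysis use is stated, and none of these tells the patient which knee to score.
- **Efficacy is secondary.** This stands, and limits the weight of the point. Section 2.1 makes safety the primary objective, and no WOMAC power or success threshold would be overturned.

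Staff may also tell patients orally which knee to rate, but the documents do not say so.

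**Conclusion.** The point holds as a risk of bias in the WOMAC efficacy analysis. The printed form can be answered for a knee that GAE did not treat, nothing in the plan prevents this, and the analysis has no means of detecting it. Dilution and inflation are both possible and the net direction is not fixed.

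On the assumed inputs, dilution is 8% to 16% at b = 0.32 and w = 0.25 to 0.50, and 0% to 38% over b = 0 to 0.75. The cited series shows only that bilateral disease is realistic.

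A reader might infer that the endpoint is known to be contaminated. The documents do not support that: if few patients enrolled have a symptomatic other knee, the effect is negligible. This is a cheap improvement that the plan should adopt; it is not a defect that invalidates the trial.

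**What to change.** 1. At the head of the Appendix D form, whenever it is completed, including screening and telephone visits, add: *Answer for your [right/left] knee, the knee treated (or to be treated) in this study.* Staff pre-fill the side. Do the same on the VAS form if it does not already name the knee.
2. Record at baseline whether the other knee is symptomatic, and record any later procedure on it, with date, on the case report form. This records care and does not restrict it.
3. State in Section 9 that the WOMAC endpoint refers to the treated knee, and add two sensitivity analyses of WOMAC change: (a) by baseline symptom status of the other knee; (b) excluding scores taken after a procedure on the other knee, with the mixed model using the remaining visits. The main model takes only baseline and 12 months, so (b) should be fitted to all scheduled visits; otherwise a patient whose 12-month score is dropped contributes no follow-up.

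**Cost.** One line on one or two forms, two case report form items and two short analyses; no extra visits.

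**Downside.** Function items such as stairs will still partly reflect the other leg, analysis (b) loses some scores, and with 40 patients the subgroups in (a) will be small and descriptive.

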#### 2.2 Secondary Objectives

The secondary objectives of this investigation are to assess efficacy using the following outcomes, compared to baseline values when appropriate:

- Improvement in pain
- Improvement in WOMAC score
- Change in radiographic imaging

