#### Angiogram:

• Temporary pain at the insertion site

Genicular artery embolization:

- Temporary discoloration of the skin (less than 2 weeks)
- Temporary soreness in the knee (less than 2 weeks)

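### Appendix D puts all 24 WOMAC items under one instruction to rate difficulty, so three of the five pain items can be answered as function

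*Combined protocol and SAP*

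**What the plan says.** Section 8.1 describes an instrument with three parts: "The WOMAC measures five items for pain (score range 0–20), two for stiffness (score range 0–8), and 17 for functional limitation". It adds that the questionnaire can be self-administered.

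The patient form in Appendix D has one instruction for all three parts. It opens "Instructions: Please rate the activities in each category according to the following", continues with a "scale of difficulty: 0 = None, 1 = Slight, 2 = Moderate, 3 = Very, 4 = Extremely", and ends "Circle one number for each activity". The items are then listed under the headings Pain, Stiffness and Physical Function; the first row reads "Pain 1. Walking". At the foot are lines for a pain subtotal (items 1 to 5) and a total.

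Section 9, Efficacy Analyses, makes WOMAC its lead outcome: "The primary is the change in WOMAC before GAE to 12 months after GAE". Section 2.2 lists "Improvement in pain" and improvement in WOMAC as separate secondary objectives. Section 5 allows the month 3, 6 or 12 visit by phone when COVID-19 travel restrictions prevent attendance.

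**The concern.** The instruction names one attribute, difficulty, while Section 8.1 assigns seven of the 24 items to two others, pain and stiffness. A patient who follows the printed instruction literally may rate how hard it is to walk in the pain block, and then rate much the same thing again in the function block. The pain subtotal would then partly measure function, and the total would count some function content twice. If a patient reads the item one way at baseline and another way later, part of the before-after change would come from the reading and not from the knee. The study has one arm, so no control group would show this, and answers already given cannot be re-asked at analysis.

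**Working it through.** **Inputs.** Appendix D: 24 items, each scored 0 to 4. Section 8.1: 5 pain, 2 stiffness and 17 function items.

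**Step 1: reproduce the plan's score ranges** (number of items × maximum item score).
- Pain: 5 × 4 = 20
- Stiffness: 2 × 4 = 8
- Function: 17 × 4 = 68
- Total: 20 + 8 + 68 = 96

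The three subscale ranges agree with Section 8.1. The scoring is sound; the question is only what the patient is asked to rate.

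**Step 2: sort the seven pain and stiffness items by how far the form itself settles the meaning.**

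| Items | What the form offers | Open to being rated as difficulty? |
|---|---|---|
| Stiffness 1 and 2 | The item text itself names stiffness | Little room |
| Pain 3 (Nocturnal), Pain 4 (Rest) | Not activities; they make sense only as pain | Little room |
| Pain 1 (Walking) | Heading only; compare Function 6, walking on the flat | Yes |
| Pain 2 (Stair Climbing) | Heading only; compare Function 1 and 2, stairs down and up | Yes |
| Pain 5 (Weight bearing) | Heading only; compare Function 4, standing | Yes |

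**Step 3: share of the score that is open to confusion.**
- Points: 3 × 4 = 12
- Share of the pain subtotal: 12 / 20 = 60%
- Share of the total score: 12 / 96 = 12.5%

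These are shares of scale points, not estimates of bias. The documents give nothing from which to compute how many patients would read the items as difficulty, or how far their answers would differ.

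**Step 4: where the wording carries most weight.** With self-administration the printed page is the only guide. By phone, the protocol supplies no text to read out for each item, and a patient may not see the block headings. The phone allowance covers months 3, 6 and 12 but not baseline, so the cue could differ between the two ends of the main efficacy contrast.

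**Step 5: reference period.** Neither Appendix D nor Section 8.1 says what period a rating covers. By contrast, the first question in Appendix G is anchored to the time since the procedure. This is missing detail. The documents do not show that patients would use different periods at different visits.

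**The case against.** The best defence is that the form makes its intent plain enough. The five items sit under the heading Pain, the foot of the page has a line for a pain subtotal, and both stiffness items name their symptom. The form is the same at every visit, so each patient meets constant wording. Pain is also measured by the VAS, which Appendix A schedules at the same visits as the WOMAC and Section 8.2 describes as a pain score. Safety is the primary objective (Sections 2.1 and 4).

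Most of this stands, and it rules out several stronger readings that a reader might infer:
- *That the pain score does not ask about pain.* The heading says otherwise, and two of the five items make sense only as pain.
- *That 28 of 96 points (29%) carry the wrong attribute.* That is the share of pain and stiffness items under the mismatched instruction. For 16 of those points (stiffness 8, Nocturnal and Rest 8) the form itself settles the meaning.
- *That the scores cannot be compared with the published WOMAC scores quoted in Section 1.* The documents do not show the form that study used, and the only literature comparison planned in Section 9 is of adverse event rates.
- *That the form departs from the licensed version 3.1 text.* That text is not reproduced outside Appendix D, so this cannot be checked.

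What the defence does not answer is the conflict between the instruction and Section 8.1 for the three remaining items. Constant wording keeps the ambiguity the same at each visit but does not remove it, and a phone visit may take away the headings on which the defence relies.

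**Conclusion.** The point holds as a minor one. Appendix D's instruction conflicts with Section 8.1, and Pain 1, 2 and 5 can be answered as difficulty. The conclusion assumes that some patients follow the instruction over the heading. If none do, the effect is nil; otherwise its size and direction cannot be computed from the documents. It is minor because WOMAC supports a secondary objective and the VAS gives a separate measure of pain. The missing reference period needs clarifying but is not an error in itself.

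**What to change.** In Appendix D, replace the single instruction with one per block, matching Section 8.1: amount of pain for the pain items, severity of stiffness for the stiffness items, degree of difficulty for the function items. Use the same text at every visit, and read it aloud when a visit is by phone. While the page is being reprinted, state one reference period, identical at baseline and all follow-up visits.

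Patients whose baseline was taken on the current form should keep it to month 12, so that a change of form is not counted as a change in WOMAC. Flag them in a sensitivity analysis, since the Section 9 model has no term for form version.

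The cost is one reprinted page and a minor amendment, with no extra visits or patients. The downside is two form versions among 40 patients if enrolment has begun.
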